8.2.2 Rescue medication

An aim of this open label study is to evaluate the safety and efficacy of Ruconest in symptomatic HAE. Therefore, it is recommended to consider administering another dose of Ruconest as a first attempt of rescue medication, which is consistent with the SPC instructions. The use of additional treatment which might interfere with the evaluation of efficacy and safety is not allowed (exclusion criterion) prior to treatment with study medication (see section 8.2.1) and after the administration of study medication for as long as possible up to 8 hours. As specified in section 10.1.3, taking such additional treatment (other than Ruconest) between the onset of the attack and prior to time of initial relief of symptoms, will qualify that attack as "treatment failure". However, appropriate and urgent medical need will not be ignored nor withheld: the use of narcotics or other standard procedures for the treatment of HAE after treatment with study medication will be allowed at the discretion of the investigator.

Situations in which the investigator may decide to install additional treatment and/or supportive measures after the administration of study medication include:

1. Clear progression of symptom severity, with or without the occurrence of symptoms at new angioedema locations.
2. Unacceptable degree of abdominal pain.
3. Symptoms indicating life is threatened (respiratory and/or cardiovascular compromise), i.e. symptoms requiring immediate additional treatment. Patients developing a life-threatening attack (e.g. a laryngeal attack with respiratory and/or cardiovascular compromise) after the administration of study medication must also be treated with any treatment procedure (including intubation, tracheostomy) deemed necessary.
4. AEs requiring specific treatment (e.g. in case of anaphylaxis).

Pain medication, anti-emetics and fluid replacement may be used in case of acute attack(s), if needed. In case of therapeutic failure, rescue therapies (such as pdC1INH) or fresh frozen plasma may be administered, according to local clinical standards.

All (escape) medications taken during acute episodes should be recorded on the CRF with indication, dose, timing and apparent response.

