#### **4.1.1.2 Visual Analogue Scale (VAS)**

VAS scores on angioedema signs and symptoms are recorded repeatedly throughout the study at the following time-points; Presentation, 30 minutes, 1, 2, 4, 8 and 24 hours.

The VAS scores are measured at up to five different locations (Abdominal, Urogenital, OPL, Facial, or Peripheral Locations), depending on the affected locations.

A series of location specific VAS assessments are taken with the last VAS question for each location indicating the overall severity of angioedema symptoms as felt by the patient for that location (0 mm corresponding to 'No symptoms' and 100 mm corresponding to 'Extremely disabling'), and is called the Overall VAS score.

**Overall VAS:** The Overall VAS score is Question 4 for attacks at Facial or Peripheral Locations, Question 5 for attacks at an Abdominal location, Question 6 for attacks at an Urogenital location and Question 7 for attacks at an OPL location.

All VAS tables will be based on the Overall VAS score for a given location, the other VAS scores will be listed only.

The Baseline Overall VAS score for each location is defined as the last non-missing measurement collected/derived prior to the first study medication administration at Time 0 hours for the attack. This would normally be the Presentation Overall VAS assessment.

The change from Baseline Overall VAS score at each post-baseline time-point will be calculated as:

Overall VAS score obtained at the specific post-baseline time-point – Baseline Overall VAS score

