## **4.1.2 Primary Efficacy Measure**

### **4.1.2.1 Time to beginning of relief based on Overall VAS**

The time to beginning of relief will be assessed using the Overall VAS score, where time of beginning of relief will be assessed as the first time point at which the VAS score decreases by at least 20mm at any eligible anatomical location compared to Baseline, with persistence of the decrease at the next time point.

The time of relief will be the first time point at which the Overall VAS score decreases by at least 20mm compared to Baseline. For example, if this was achieved at 2 hours with persistence shown at 4 hours then the time of beginning of relief of symptoms will be 2 hours.

Patients who do not have beginning of relief during the time that they are followed-up will be censored at the last time at which the Overall VAS score is recorded at any eligible anatomical location. Note: If a patient was randomized but did not have any post-baseline efficacy data then they will be censored at Presentation. Patients who first have a decrease of  $\geq 20$ mm at the last time Overall VAS score was recorded will not have achieved beginning of relief with persistence. Therefore, they will be censored at the penultimate time that Overall VAS was recorded.

Time to beginning of relief (minutes) will be calculated as:

Actual date and time of first relief (or date and time of censoring) – Date and time of the Baseline Overall VAS assessment

The actual date and time of beginning of relief will be used in the calculation.

The beginning of relief assessed using Overall VAS will be assessed for the first eligible location at which time to beginning of relief of symptoms by Overall VAS first occurred. Only locations with a populated start date and time and corresponding Overall VAS will be used for the calculation of time to beginning of relief.

For the evaluation of persistence, the decrease of  $\geq 20$ mm is required at the next assessment time for which the Overall VAS score is not missing. For example, if 2 Overall VAS determinations with  $\geq 20$ mm decline from Baseline are separated by a missing scheduled assessment then beginning of relief with persistence would have still been achieved.

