## **4.1.3 Secondary Efficacy Measures**

### **4.1.3.1 Time to minimal symptoms based on Overall VAS**

The time of minimal symptoms for an attack assessed using the Overall VAS is defined as the time at which the Overall VAS score falls below 20mm for all locations where VAS Scores are recorded.

- Patients who do not have minimal symptoms during the time that they are followed-up will be censored at the last time at which an Overall VAS score is recorded. Note: If a patient was randomized but did not have any post-baseline efficacy data then they will be censored at Presentation.
- A worst-case scenario will be used to impute missing Overall VAS scores for locations. If there are 2 non-missing values either side of missing value(s) then last observation carried forward (LOCF) or next observation carried backward (NOCB) will be used to carry forward or back the largest Overall VAS. If there is only one Overall VAS followed by missing values or after missing values it will be carried forward or back. If the Overall VAS score for a location is blank at Baseline, but then the location is affected by angioedema

post-dosing, a score of 0 will be imputed for all post-baseline time-points up until the first documented Overall VAS score. The worst-case scenario method will then be applied for all subsequent missing Overall VAS scores.

- The time to minimal symptoms for patients who receive disallowed concomitant medication will be censored at the last time at which the patient had an Overall VAS score prior to their receipt of disallowed concomitant medication. If this is Presentation and hence prior to study drug administration then the time to minimal symptoms will be censored at time 0 minutes.

Time to minimal symptoms (minutes) will be calculated as:

Actual date and time of minimal symptoms (or date and time of censoring) – date and time of the Overall VAS assessment at Baseline

Time of the actual date and time of minimal symptoms will be used in the calculation.

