#### **4.1.4.6 Therapeutic failure**

A patient will be assessed as having had a therapeutic failure if any of the following occurs:

- Time to the beginning of relief of symptoms for the attack based on the Overall VAS occurs later than 4 hours after Baseline.
- Within 4 hours after beginning of treatment administration and after beginning of relief, the Overall VAS increases again to a value of at least the Baseline score.
- The patient has occurrence of HAE at a new location within 4 hours after achieving beginning of relief of symptoms (Based on an IS score of greater than 0 at a new location that had an IS score of 0 at Baseline). Beginning of relief of symptoms here is based on the Overall VAS as defined in Section 4.1.2.1.
- The patient taking any of the medications that may interfere with the assessment of the impact of Ruconest on efficacy measures, between the onset of the attack and prior to time of initial relief of symptoms including:
  - Narcotics
  - Plasma-derived C1 inhibitor
  - Fresh frozen plasma
  - Bradykinin receptor antagonist
  - Analgesics
  - Anti-emetics
  - Non Steroidal Anti-Inflammatory Drugs (NSAIDs)
  - Paracetamol (within 45 minutes before the administration of Ruconest)

The medical monitor will perform a manual review of the concomitant medications and identify those which fall into the above categories.

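### Interfering medication taken between the first 20 mm VAS fall and its confirmation is not a therapeutic failure, and may itself supply the confirmation

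*SAP*

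**What the plan says.** Relief on the Overall VAS (SAP 4.1.2.1) needs a fall of at least 20 mm from Baseline at an eligible location that is still present at the next non-missing VAS. Its time is that of the first fall: "achieved at 2 hours with persistence shown at 4 hours then the time of beginning of relief of symptoms will be 2 hours". The section has no rule for interfering medication.

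SAP 4.1.4.6 gives four criteria for therapeutic failure, any one of which is enough:

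1. VAS relief later than 4 h after Baseline.
2. After relief, and within 4 h of the start of treatment, a VAS back to at least Baseline.
3. A new location within 4 h after relief.
4. Interfering drugs taken "between the onset of the attack and prior to time of initial relief of symptoms including" those on a list such as narcotics, pdC1INH and fresh frozen plasma.

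Protocol 10.1.3 has the same fourth criterion. Protocol 8.2.2 repeats its window for "taking such additional treatment (other than Ruconest) between the onset of the attack and prior to time of initial relief of symptoms".

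Time to minimal symptoms treats the same drugs differently. Under SAP 4.1.3.1, patients who receive them "will be censored at the last time at which the patient had an Overall VAS score prior to their receipt of disallowed concomitant medication". SAP 4.1.4.5 does the same for complete resolution.

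**The concern.** Relief is not established until the confirming VAS, but criterion 4 stops counting drugs at the back-dated first fall. Between the two, a child can receive another HAE treatment or a narcotic without the attack becoming a failure. The confirming score is then taken under that drug, and an effective rescue can turn an unconfirmed fall into confirmed relief with Ruconest. The SAP does not use a VAS taken after such medication for minimal symptoms, yet accepts it as proof of persistence.

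Two results are affected: the therapeutic failure percentage and VAS time to beginning of relief, which the SAP calls its primary efficacy measure. In a single-arm descriptive study of about 20 children, readers will rely on such figures.

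**Working it through.** **Inputs.** VAS times are "Presentation, 30 minutes, 1, 2, 4, 8 and 24 hours" (SAP 4.1.1.2). The relief rule is in SAP 4.1.2.1 and the failure criteria in 4.1.4.6. The Baseline VAS is completed just before infusion (Protocol 10.2.3). The 4 h VAS may deviate by 24 min either way, counted from the start of administration (Protocol 10.2.4.2). The target is at least 20 patients (SAP 2.3). Neither document gives a rescue rate or an expected failure rate, so there is no planned figure to reproduce. The VAS paths below are assumed: one location, Baseline 80 mm.

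**Step 1: length of the gap.** Gap = time of the confirming VAS minus time of the first fall. The last column shows the scheduled VAS readings, after confirmation and up to 4 h, at which criterion 2 can still apply at the location that defined relief.

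| First fall | Confirming VAS | Gap | Criterion 2 can apply at |
|---|---|---|---|
| 0.5 h | 1 h | 1 − 0.5 = 0.5 h | 2 h, 4 h |
| 1 h | 2 h | 2 − 1 = 1 h | 4 h |
| 2 h | 4 h | 4 − 2 = 2 h | none |

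A first fall at the 4 h VAS would nominally leave 8 − 4 = 4 h. However, time runs from the pre-infusion Baseline VAS, so that relief is later than 4 h after Baseline unless the form is completed early. Criterion 1 then usually makes it a failure already. A missing VAS lengthens the gap, because persistence is judged at the next non-missing score: with a fall at 2 h and the 4 h score missing, the gap is 8 − 2 = 6 h.

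**Step 2: rescue before confirmation.** VAS values are at 0.5, 1, 2, 4, 8 and 24 h.

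- Path A: 80, 75, 55, 50, 30, 10, with pdC1INH at 3 h. The fall at 2 h is 80 − 55 = 25 mm, and at 4 h it is 80 − 50 = 30 mm. Relief is dated 2 h, the drug at 3 h comes after it, and no other criterion applies: **no failure**.
- Path B: 80, 75, 55, 70, 50, 30, without rescue. At 4 h the fall is only 80 − 70 = 10 mm, so the 2 h fall does not persist. Falls of 30 mm at 8 h and 50 mm at 24 h date relief at 8 h, later than 4 h: **failure** under criterion 1.

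The two paths agree up to 2 h. If the window ended at the confirming VAS, path A would be a failure, because 3 h is before 4 h.

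**Step 3: rescue after confirmed relief.**

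- Path C: 55, 55, 80, 50, 30, 10, rescue at 2.5 h. The VAS is back at Baseline at 2 h: **failure** under criterion 2.
- Path D: 55, 55, 75, 40, 30, 10, rescue at 2.5 h. The return stops short of Baseline: **no failure**.
- Path E: 75, 55, 50, 50, 80, 20, rescue at 8.5 h. The return is seen at 8 h, outside criterion 2's 4 h limit: **no failure**.
- Path F: 55, 50, 50, 40, 20, 10, with return and rescue at 2.5 h, between readings. No VAS records the return: **no failure**.

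In D, E and F relief was confirmed (at 1, 2 and 1 h) before the rescue, so moving the window to confirmation does not change them.

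**Step 4: size.** One reclassified patient among 20 first attacks is 1/20 = 5 percentage points. Starting from an assumed 0 failures, the exact 95% intervals are:

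| Failures | Rate | 95% CI |
|---|---|---|
| 0/20 | 0% | 0 to 16.8% |
| 1/20 | 5% | 0.1 to 24.9% |
| 2/20 | 10% | 1.2 to 31.7% |
| 4/20 | 20% | 5.7 to 43.7% |

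**The case against.** The strongest reply is that the SAP does what the protocol asks. The window is the same in Protocol 10.1.3 and 8.2.2, the endpoint is exploratory, and SAP 5.2 plans no hypothesis test. That stands: this is a weak definition, not a departure from the protocol. It is also true that failure status and concomitant medication are listed per patient (Listings 16.2.6.1.4 and 16.2.4.5), so a careful reader could trace such a case. The reported percentage would still not show it.

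Four stronger readings are tempting, and the documents do not support them.

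- A reader might infer that any attack rescued when it returns escapes. Criteria 2 and 3 already capture a recorded return to Baseline within 4 h of treatment and a new location within 4 h of relief, with or without rescue (path C). Only partial, later or unrecorded returns escape (paths D, E and F).
- A reader might infer that such an attack counts against the drug nowhere. SAP 6.7.4 also reports the percentage of patients with each event, and an attack censored for minimal symptoms or complete resolution is a non-event there.
- Protocol 8.2.2 bars interfering treatment "after the administration of study medication for as long as possible up to 8 hours". A reader might treat those 8 h as the failure window and the part after relief as the size of the bias. The text restricts conduct, and the next sentence ends the failure window at initial relief. A share of clock time does not measure misclassification.
- Protocol 8.2.2 also says "In case of therapeutic failure, rescue therapies (such as pdC1INH) or fresh frozen plasma may be administered". That permits rescue after failure; it does not make every rescue a failure.

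A fair objection to the remedy is that an analgesic or anti-emetic taken after a large fall but before the next form would count as failure, although Protocol 8.2.2 allows these if needed. That is a real cost, but the same drugs already count when taken before the first fall.

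**Conclusion.** The point holds for medication taken between the first 20 mm fall and the VAS that confirms it, a gap of about 0.5, 1 or 2 h on the planned schedule. Such an attack is not a therapeutic failure unless another criterion applies, and the drug may have produced the confirmation. Any resulting error lowers the failure percentage and favours VAS time to beginning of relief; in paths A and B, relief is dated 2 h instead of 8 h. How many attacks are affected cannot be derived from the documents.

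This rests on reading the time of initial relief in criterion 4 as the VAS time of SAP 4.1.2.1. The explicit cross-reference is in criterion 3 only, but no other definition is offered. The medical monitor's review in 4.1.4.6 assigns drugs to categories and does not extend the window. Whether rescue after confirmed relief should also be a failure is debatable, and the main definition need not change for it.

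**What to change.** - **SAP 4.1.4.6, criterion 4:** end the medication window at the VAS assessment that confirms relief. For this purpose use the confirming VAS as 4.1.2.1 identifies it today, so that this change and the next are not circular.
- **SAP 4.1.2.1:** do not accept a VAS taken after listed medication as confirmation. Censor at the last VAS before the medication, as in 4.1.3.1, and say that this takes precedence over the existing rule for an unconfirmed fall at the last recorded VAS, which would censor one assessment earlier.
- **Tables 14.2.1.8.1 and 14.2.1.8.2:** show the protocol definition as a comparison line. Add a supplementary row for pdC1INH, fresh frozen plasma or a bradykinin receptor antagonist given for the same attack after confirmed relief, without counting it in the main definition.
- **Drug list:** Protocol Appendix F lists recombinant human C1 inhibitor among the failure medications, 8.2.2 exempts Ruconest, and the lists in Protocol 10.1.3 and SAP 4.1.4.6 omit it. These passages must be reconciled.
- **Declaration:** SAP 7.1, or the clinical study report if the database is locked. The SOP deviation form attached to the SAP says the analysis has been finalised, so the report is the likely place.

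The cost is SAP wording, a derived flag from medication times already collected, and the extra table lines. The failure rate and time to relief may look slightly less favourable, and analgesics or anti-emetics taken before confirmation would also count. No patient's treatment changes.

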#### **4.1.4.7 Receipt of a second dose**

The number of patients who received two doses of rhC1INH as treatment for a single HAE attack will be assessed. For each HAE attack the following will be presented:

- The number of patients who received a second dose;
- The Baseline Overall VAS score at the primary attack location, split by attacks treated with a second dose and those that were treated with a single dose.

## **4.2 Safety Measures**

The primary objective of the study is the assessment of safety and tolerability as evaluated by recording of adverse events (AEs) and immunogenicity parameters (anti-HRI, anti-rhC1, anti rabbit epithelium IgE).

#### **4.2.1 Exposure to Study Medication**

Patients up to 84 kg will receive one i.v. injection of Ruconest at a dose of 50 U/kg. Patients of 84 kg body weight or greater will receive one i.v. injection of Ruconest at the dose of 4200 U (2 vials). At the discretion of the investigator and depending upon the patient's clinical response, an additional dose may be given to patients following their initial dose as specified above. No more than two doses should be administered within 24 hours.

The following variables will be calculated for each attack and dose. They will be presented separately for the initial and second dose:

- Total volume of medication administered (mL)
- Total Dose in U/kg (patients who weighed less than 84 kg)
- Total Dose in U/kg (patients who weighed more than or equal to 84 kg)
- Duration of Infusion in minutes (only summarized for Attack 1)

Duration of Infusion will be calculated as:

Stop time of last injection – Start time of first injection (for each attack)

For patients who received a second injection for the same attack, the duration of exposure will be calculated as the sum of the duration of exposure for the first and second doses for the attack.

In addition, the following variables will also be calculated:

- Was the total volume of medication administered ('Yes' or 'No')
- Did the patient received a second dose ('Yes' or 'No')
- Did the patient receive a second dose for any of their attacks? (Yes/No – summarized over all attacks)
- Time interval between initial and repeat dose (minutes)
  - Date and time of start of repeat dose - Date and time of end of initial dose

The following endpoints will also be calculated:

- Total number of HAE attacks treated with rhC1INH during the study (categorical and continuous summaries)
- Total number of rhC1INH doses received during the study (categorical and continuous summaries)
- Total dose of rhC1INH received in U/kg (continuous summary)

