**Table 1 Study Treatments**

Actual Treatment	Treatment Label
One i.v. injection of Ruconest (weight adjusted dose)	Ruconest

Table 2 presents the visit labels that will be used in all output.

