#### **6.7.6 Receipt of a Second Dose**

The number of patients who received a second dose will be summarized using counts and percentages. The Baseline Overall VAS score at the primary attack location, split by attacks treated with a second dose and those that were treated with a single dose, will be summarized using summary statistics.

This will be presented by attack number. In addition, a total column will be presented summarizing all attacks. If a patient has more than one attack they will be included multiple times in this column.

Finally the summary will present the number of patients who had received two doses of rhC1INH for any of their attacks.

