### 6.9.2.1 PK and PD Concentrations

To assess the single dose PK and PD profiles, PK and PD concentrations will be listed, summarized and plotted for patients in the PK/PD Concentration Set, where missing and BLQ values will be handled as detailed in Section 6.9.2.1.1.

Functional C1INH (PK) concentrations will be in units of % of Normal (i.e. results are expressed as a percent based on a pool of plasma collected from healthy volunteers, which was original set at 100%) whereas C4 concentrations will be in units of  $\mu\text{g}/\text{mL}$ .

The Baseline concentration is defined as the concentration taken at Presentation.

Summaries and figures will include:

- Listing of all PK and PD concentrations sorted by, patient ID and nominal time post-dose. The listings of concentrations will include the actual sample collection times, the time of dosing and deviations from the nominal time.
- A summary of concentrations by nominal time post-dose, where the set of statistics will include n, mean, geometric mean, median, SD, coefficient of variation (CV) Geometric CV, minimum, maximum and the number of concentrations above the LLQ.
- Boxplots of concentrations paneled by nominal time, presented separately on linear and logarithmic scales.
- Boxplots of concentrations grouped by weight and paneled by nominal time, presented separately on linear and logarithmic scales.
- The ratio (2-4 hours:Baseline) in C4 versus the ratio (2-4 hours:Baseline) in Functional C1INH.

The subgroups for weight for the boxplots of concentrations will be:

- 1) Weight  $\leq 30\text{kg}$
- 2)  $30\text{kg} > \text{Weight} \geq 60\text{kg}$

- 3) 60kg > Weight  $\geq$  84kg
- 4) Weight > 84kg

Paneling by weight will only be performed if there are a sufficient number of patients in each subgroup.

The range for the x-axes of these plots will be decided on review of the data, and will depend on how long the concentration is quantifiable in the matrix.

For summary statistics and boxplots by sampling time, the nominal PK/PD sampling time will be used.

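### The SAP does not settle how attacks given a second dose are analysed: infusion duration has conflicting rules, PK has no explicit rule, and pooled relief is not split by second dose

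*SAP*

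**What the plan says.** A second dose is a planned option. Protocol 8.1 and SAP 2.2 allow it at the investigator's discretion according to response, with at most two doses in 24 hours and no stated earliest time. Footnote 1 to the schedule foresees the catheter staying in for 4 hours and serving a second dose.

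- **Duration (SAP 4.2.1).** The formula is "Stop time of last injection – Start time of first injection (for each attack". For attacks with a second injection, "the duration of exposure will be calculated as the sum of the duration of exposure for the first and second doses for the attack". The lead-in to the list of variables says "They will be presented separately for the initial and second dose". The gap has its own variable: "Date and time of start of repeat dose - Date and time of end of initial dose".
- **PK/PD (SAP 6.9.2).** "To assess the single dose PK and PD profiles, PK and PD concentrations will be listed, summarized and plotted". Cmax is the highest C1INH value in the first attack and is derived only if all three samples exist. AUC0-3 runs to the 2-4 h sample. Neither rule mentions a second dose.
- **Relief (SAP 4.1.2.1 and 6.7.6).** Relief is the first persistent fall of at least 20 mm in Overall VAS at any eligible location, with no provision for a second dose. SAP Table 1 describes the only treatment as "One i.v. injection of Ruconest (weight adjusted dose", labelled Ruconest in all output. By number of doses, SAP 6.7.6 gives patient counts and one split: "The Baseline Overall VAS score at the primary attack location, split by attacks treated with a second dose".
- **Therapeutic failure.** Protocol Appendix F lists recombinant human C1 inhibitor among the medicines that make an attack a failure if taken before relief. Protocol 8.2.2 exempts Ruconest. Protocol 10.1.3 and SAP 4.1.4.6 leave it off their lists.

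**The concern.** The usual reason for a second dose is a poor response in the first hours, and the 2-4 h PK sample and most of the VAS readings fall in or after those hours. So the attacks in which these rules matter are not a random subset.

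Three outputs are exposed. Two programmers could each follow SAP 4.2.1 and report different durations for the same attack. An AUC0-3 presented as single-dose exposure could contain two doses. A time-to-relief curve would also not show how much of the relief followed the initial dose alone. Baseline VAS cannot fill that last gap, because it is measured before either dose.

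The failure definitions add to this: the same child, relieved only after a second dose, is a failure under one passage and need not be under the others.

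**Working it through.** The plan gives no figure of its own on this point, so there is none to reproduce. The sizes below rest on stated assumptions.

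**1. Duration.** One injection lasts about 5 minutes (Protocol 8.1). The gap g is assumed.

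- Last stop minus first start: 5 + g + 5
- Sum of injections: 5 + 5 = 10
- Per dose: 5 and 5

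The first exceeds the second by exactly g. The group means take 20 children, one of them with two doses.

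| Gap (min) | Last minus first (min) | Sum (min) | Mean, last minus first | Mean, sum |
|---|---|---|---|---|
| 60 | 70 | 10 | (19×5 + 70)/20 = 8.25 | (19×5 + 10)/20 = 5.25 |
| 120 | 130 | 10 | (19×5 + 130)/20 = 11.25 | 5.25 |
| 240 | 250 | 10 | (19×5 + 250)/20 = 17.25 | 5.25 |

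Shown per dose, the mean for the initial dose is 5.0.

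**2. PK.** Assumed profile:

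- Baseline 20% of normal, the type I median in Protocol 4.1.
- 136% at 5 min, from the adult peak of 1.36 U/mL after 50 U/kg in Protocol 9.3. That section gives the normal range both as 0.7-1.3 U/mL and as 70-130%.
- 45% at 3 h, an assumption between about 70% at 2 h and baseline at about 4 h in the same adult data.

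The SAP's linear-up log-down rule gives:

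- 0 to 5 min: (20 + 136)/2 × 5/60 = 6.5
- 5 min to 3 h, one dose: (136 − 45)/ln(136/45) × 2.917 = 240.0. Total 246.5 %·h.
- A second dose adds 70 points at 3 h (115%): (136 − 115)/ln(136/115) × 2.917 = 365.2. Total 371.7 %·h, or +51%.
- A second dose adds the full 116 points (161%): (136 + 161)/2 × 2.917 = 433.1. Total 439.6 %·h, or +78%, and the late sample becomes Cmax.

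If one child in 20 is affected and all share the same single-dose value, the mean moves by 51%/20 = 2.5% to 78%/20 = 3.9%.

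As a cross-check I used exponential decline from 1.36 U/mL at 5 min to 0.7 U/mL at 2 h, with baseline 0 to 0.3 U/mL, late sample at 2 to 4 h and second dose at 0.5 to 2.5 h. The child's AUC is multiplied by 1.16 to 1.75, so a mean of 20 moves by 0.8% to 3.75%. Cmax changes only when the late sample exceeds the 5-minute one. A second dose after the late sample changes nothing.

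**3. Relief and failure.** Take a child with no relief at 1 h, a second dose soon after, and persistent relief from 2 h.

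| Passage | How this child is handled |
|---|---|
| SAP 4.1.2.1 | Relief event at 2 h, pooled with one-dose relief |
| SAP 6.7.6 | Counted as a second-dose recipient; only baseline VAS shown by number of doses |
| Protocol Appendix F | Therapeutic failure |
| Protocol 8.2.2 | Not a failure on this ground: Ruconest exempt |
| Protocol 10.1.3, SAP 4.1.4.6 | Recombinant C1 inhibitor not listed |

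In a first-attack analysis of 20 children, each such child is 1/20 = 5 percentage points of the proportion relieved.

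**The case against.** The strongest reply is that the SAP does deal with the second dose. In SAP 4.2.1 the sum sentence can be read as a specific override of a general formula. Values per dose are requested there and again in 6.8.1, and the gap has its own variable. For PK, 6.9.2.1.1 lets the pharmacokineticist flag anomalous values. SAP 6.9.2.2 leaves estimates known to be biased out of the statistics and gives an unexpected event only as an example. For relief, the objective concerns Ruconest as treatment of an attack, and the protocol makes a second dose part of that treatment. Time is counted from the baseline VAS before the first dose, so the clock is not restarted. Efficacy is secondary and descriptive, with no hypothesis test.

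Much of this stands. A reader might infer that the reported duration does include the gap, that two-dose PK will certainly be summarised as single-dose, or that relief is presented as the result of one injection. The documents do not support any of these. The duration is undetermined rather than wrong. Affected PK could be removed at data review. The output is labelled Ruconest, and pooling fits the protocol's view of therapy.

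What remains is that the last-minus-first formula is still in the text. The PK exclusions depend on judgement and do not name a permitted second dose. No planned summary separates relief before a second dose from relief after it.

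**Conclusion.** The point holds as a set of unspecified or conflicting analysis rules, not as proof of wrong results. The duration conflict is real but minor. The PK gap can matter for an individual child: about +50% to +80% in AUC0-3 on the main assumptions, and as little as +16% on the cross-check. It has a small effect on a mean of 20 (about 2.5% to 4%, or under 1% at the low end), and it arises only if the second dose precedes the late sample in attack 1. The relief split matters most, because it concerns the SAP's primary efficacy measure and the documents disagree on whether the same event is a failure. The frequency and timing of second doses are not in the documents, so the actual effect on any output is unknown.

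**What to change.** 1. **Duration.** Delete the last-minus-first formula in SAP 4.2.1. Report duration per injection, and the sum where a total is wanted.
2. **PK/PD.** For single-dose summaries, set C1INH and C4 values taken after the start of a second dose to missing and do not derive AUC0-3 for that child. Amend the three-sample rule in SAP 6.9.2.2 so that Cmax may come from the samples before the second dose. Without that, Cmax is lost and SAP 3.6 drops the child from the PK/PD Analysis Set.
3. **Relief.** Keep the planned pooled analysis. Add to Table 14.2.1.9, by attack, the number with VAS relief before any second dose and the number with relief only after it. Add a supportive Kaplan-Meier analysis in which a second dose before relief counts as not relieved to the end of observation. Censoring at the second dose would not serve, because re-dosing is itself a sign of poor response.
4. **Failure.** Reconcile Protocol Appendix F, 8.2.2 and 10.1.3 with SAP 4.1.4.6.

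Dose and assessment times are already recorded. The SOP deviation form attached to the SAP says that the analysis is finished, so any of this done now belongs in the clinical study report, labelled post hoc, in line with SAP 7.5. The cost is a few extra rows, the loss of AUC0-3 for perhaps one or two children, and a supportive relief figure that may be less favourable.
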